4.0 ELIGIBILITY CRITERIA

4.1 Inclusion Criteria

- Male or female subjects aged 18-75 years old inclusive
- Meet Rome IV criteria for IBS-D or IBS-M
- Subjects should report urgency with bowel movement at least once a week
- If subjects are ≥50 years old, a colonoscopy must have been completed within the past 5 years
- Subjects are capable of understanding the requirements of the study, are willing to comply with all the study procedures, and are willing to attend all study visits.
- Agree to use an acceptable method of contraception throughout their participation in the study. Acceptable methods of contraception include:
 - double barrier methods (condom with spermicidal jelly or a diaphragm with spermicide),
 - hormonal methods (e. g. oral contraceptives, patches or medroxyprogesterone acetate), or
 - an intrauterine device (IUD) with a documented failure rate of less than 1% per year.
 - Abstinence or partner(s) with a vasectomy may be considered an acceptable method of contraception at the discretion of the investigator.
 - All subjects will provide Institutional Review Board (IRB)-approved informed written consent prior to beginning any study-related activities

NOTE: Female subjects who have been surgically sterilized (e.g. hysterectomy or bilateral tubal ligation) or who are postmenopausal (total cessation of menses for >1 year) will not be considered "females of childbearing potential".

4.2 Exclusion Criteria

- Treatment with antibiotics or Xifaxan in the last two months
- Subjects with history of intestinal surgery (except appendectomy or cholecystectomy)
- Subjects with known pelvic floor dysfunction
- Pregnancy

- Nursing mothers
- Poorly controlled/uncontrolled significant medical condition that would interfere with study procedures
- History of bowel obstruction
- History of celiac disease
- History of inflammatory bowel disease
- Cirrhosis
- IBS-C/chronic idiopathic constipation
- Poorly controlled diabetes (hemoglobin A1c >8.0% for ≥1 year) ²⁹
- History of anorectal radiation/surgery
- History of prostatitis
- Known allergy or hypersensitivity to rifaximin or rifamycin
- Current treatment with eluxadoline or opiates

NOTE: Development of any of the exclusion criteria during the study will be considered a basis for subject discontinuation.

5.0 INVESTIGATIONAL PRODUCT

5.1 Formulation and Supply

Xifaxan will be supplied by Salix pharmaceuticals. Xifaxan is approved by FDA to be used in patients with IBS-D, hepatic encephalopathy and *E. coli*-associated traveler's diarrhea.

5.2 Packaging

On day 0 (see section 6.0 – Study Procedures and Regimens), subjects will be provided medication packs sufficient for 14 days.

For all study investigational product, a system of investigational product numbering in accordance with all requirements of current Good Manufacturing Practice (GMP) will be used. This will ensure that for each subject, any measured quantity of study investigational product can be identified and traced back to the original pack of medication.

Lists linking all numbering levels will be maintained by the institutions in charge of investigational product packaging including the Sponsor.

5.3 Labeling

Each pack will bear a label which includes, but is not limited to, the following information:

- Product: Xifaxan
- Kit Number
- Quantity
- Instructions for taking product
- Storage conditions: Store packets/kit at 20-25°C (68-77°F): excursions permitted between 15-30°C (59-86°F)
- Manufacturer

In addition, each kit label will contain an area for the site to write the following information:

- Subject initials
- Subject ID Number
- Date Dispensed

- Date Returned

5.4 Storage and Handling

All investigational product will be kept in a locked area with limited access to study staff only. The locked area will be maintained under controlled temperature conditions at 20-25°C (68-77°F); excursions are permitted to 15-30°C (59-86°F).

5.5 Rationale for Xifaxan dose selection

Currently, Xifaxan is approved for treatment of IBS-D. The dosing is 550 mg PO TID for 14 days. In addition, two 14-day retreatment courses of Xifaxan is allowed by FDA if the patient does not respond to initial therapy. We have designed our study so that subjects will receive one standard 14-day course of Xifaxan during the study. This is less than the three courses of Xifaxan allowable for IBS-D patients per the FDA.

6.0 STUDY PROCEDURES AND REGIMENS

6.1 Subject identification and recruitment

Potential subjects with IBS-D and IBS-M will be identified through the GI Motility Clinic at Cedars-Sinai Medical Center and assessed for eligibility to participate in this study.

6.2 Therapy phase

If patients meet the inclusion criteria and provide informed written consent, they will:

Visit 1: Day -7	-	Undergo a urine pregnancy test (if a woman of childbearing potential)
	-	Complete a baseline symptom questionnaire (see Appendix 1).
		This can either be filled online using REDCap, a secure, web-
		based application for building and managing online surveys and
		databases with which Cedars-Sinai is partnered, or completed in paper format
	-	Present fasting for a full lactulose breath test (see Appendix 2)
	-	Up to 60 cc of exhaled breath gas at baseline and 120 minutes of
		testing will be stored for additional testing by mass spectroscopy
		(Exetainer® 12ml flat-bottom vacuumed vials, LabCo, UK).
	-	Subjects will be given a stool diary (see Appendix 3) and asked to
		complete this at home over the next 7 days, using the Bristol Stool
		Chart (see Appendix 4) as a visual aid
	-	Patient will undergo a rectal sensitivity assessment (Appendix 5)
Day -7 to Day 0	-	Complete a 7-day baseline stool and symptom diary (see
		Appendix 3) using the Bristol Stool Chart (see Appendix 4)
Visit 2: Day 0	-	A 14-day supply of Xifaxan will be provided to the patient
	Ea	ch subject will be instructed by the investigator or his
	rep	presentative on the proper self-administration, handling and storage
	of	the product. Each subject will be instructed to take Xifaxan 550 mg
	PC	O TID for 14 days. For the purpose of accountability, all unused

14

packets from each kit dispensed to the subject should be returned to the site at each visit. In order to maintain compliance with federal regulations, records of the disposition of drug will include: dates dispensed, quantity, use by the subject and dates of returns.

- Day 0 to Day 14
 Subjects will complete weekly symptom questionnaires (see

 Appendix 6) at home, beginning on Days 0 and 7. Again, these
 can either be filled online using REDCap, or completed in paper

 format
 - Subjects will complete a Daily Stool Diary (see Appendix 3)
- *Visit 2: Day 15* Subject will undergo a rectal sensitivity assessment (Appendix 5)
 - Subject will undergo an LBT
 - Up to 60 cc of exhaled breath gas at baseline and 120 minutes of testing will be stored for additional testing by mass spectroscopy (Exetainer® 12ml flat bottom vials, LabCo, UK).

6.3 Study Flowchart

6.4 Study Duration

The study duration will be approximately 1 year. Each subject will be involved in the study for 3 weeks (see Study Flowchart).

6.5 Medications Not Permitted

The following medications may not be taken while on this study:

- Opiates or new pain modulating medications
- Eluxadoline

7.0 OUTCOME MEASURES

7.1 Primary Outcome Measure

The primary outcome of the study is the mean change in the balloon volume that leads to first urge to defecate. A 100-mm visual analogue scale with verbal descriptors (0=no sensation, 20=first sensation, 40=first sense of urge, 60=normal urge to defecate, 80=severe urge to defecate, and 100=discomfort/pain) will be used to score evoked sensations ³⁰.

7.2 Secondary Outcome Measures

Secondary outcome measures will include:

- mean change in the balloon pressure and volume that leads to first urge to defecate
- mean change in the balloon pressure and volume that leads to severe urge to defecate
- mean change in the balloon pressure and volume that leads to severe urge to defecate
- mean change in the balloon pressure and volume that leads to severe urge to defecate
- mean change in the balloon pressure and volume that leads to first sensation
- mean change in the balloon pressure and volume that leads to first sensation
- mean change in the balloon pressure and volume that leads to first sensation
- Association of urgency symptom and rectal sensitivity testing
- Normalization of LBT as a predictor of improvement of rectal hypersensitivity

8.0 SIDE EFFECTS

All side effects will be captured, evaluated and categorized as follows:

- An Adverse Event (AE) will be a side effect that is an event reported by the subject that is deemed related to Xifaxan but may or may not prevent continuation of the trial (examples include body aches, loose stool)
- A Serious Adverse Event (SAE) will be an event report by a subject during the trial may or may not be deemed related to Xifaxan that forces discontinuation of the trial (examples include anaphylaxis, etc.).

All side effects will be reported to a data safety monitor who is independent of the study.

The assessment of the relationship of an AE to the administration of the study medical food supplement is a clinical decision based on all available information at the time of the completion of the source documentation of the AE or of the SAE form, if applicable.

An assessment of "Not" or "Unlikely" would include (Note: "Unlikely" is considered not related to the study medical food supplement):

- The existence of a clear alternative explanation, e.g., mechanical bleeding at surgical site; or
- Non-plausibility, e.g., the subject is struck by an automobile when there is no indication that the study medical food supplement caused disorientation that may have caused the event; cancer developing a few days after the first therapy administration.

An assessment of "Possible" or "Related" indicates that there is a reasonable suspicion that the AE is associated with the use of the study medical food supplement.

Factors to be considered in assessing the relationship of the AE to the study medical food supplement include:

- The temporal sequence from administration of the study medical food supplement:
 The event should occur after the therapy is given. The length of time from therapy exposure to event should be evaluated in the clinical context of the event.
- Recovery of discontinuation (de-challenge), recurrence on re-introduction (rechallenge): Subject's response after discontinuation of the study medical food supplement (de-challenge), or response after re-introduction of the study medical

food supplement (re-challenge) should be considered in the view of the usual clinical course of the event in question.

- Underlying, concomitant, intercurrent diseases: Each report should be evaluated in the context of the natural history and course of the disease being treated and any other disease the subject may have.
- Concomitant medication or treatment: The other therapies the subject is taking or the treatment the subject receives should be examined to determine whether any of them may be suspected to cause the event in question.
- Concurrent study procedures: Study procedures should also be considered as possible causes of an AE. Invasive procedures such as biopsies have their own profile of expected AEs and the Investigator should consider these.

The Investigator will make a separate and independent assessment of every AE's relationship not just to the study the study medical food supplement, but also to the subject's pre-existing medical condition(s).

The severity of AEs should be graded as follows:

- Mild usually transient in nature and generally not interfering with normal activities
- Moderate sufficiently discomforting to interfere with normal activities
- Severe prevents normal activities

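### Section 8.0 makes relatedness to Xifaxan and report by the subject conditions for being an AE, which contradicts its own causality assessment and, read literally, leaves non-discontinuing procedural, unrelated and staff-observed events outside the AE and SAE record

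*Combined protocol and SAP*

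**What the plan says.** Section 8.0 opens with "All side effects will be captured, evaluated and categorized as follows" and then gives two definitions.

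- An AE is a side effect, described as "an event reported by the subject that is deemed related to Xifaxan but may or may not prevent continuation of the trial".
- An SAE is an event reported by a subject that "may or may not be deemed related to Xifaxan that forces discontinuation of the trial".

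The causality text follows in the same section. It offers four outcomes: *Not*, *Unlikely*, *Possible* and *Related*. The first two are introduced by "An assessment of 'Not' or 'Unlikely' would include" and illustrated by clearly unrelated events, such as a road accident. On procedures it says: "Study procedures should also be considered as possible causes of an AE". It also states: "The Investigator will make a separate and independent assessment of every AE's relationship", meaning the relationship to the study product and to pre-existing conditions. Throughout, this text calls the product a medical food supplement, not Xifaxan.

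Section 6.2 places the first balloon test and the first lactulose breath test at Visit 1 (Day -7), the supply of Xifaxan at Day 0, and the second pair of tests at Day 15. Section 8.3 requires follow-up of all AEs and SAEs.

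**The concern.** Relatedness should be assessed after an event has been recorded. Here it decides whether the event is recorded as an AE at all, and the definition does not say who makes that judgement or when. The requirement that the subject report the event is a second filter, and nothing in the visible text provides for findings made by staff.

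The study has one arm and is open-label, so no comparison group would reveal an under-count. The graded balloon distention, up to 200 cc under Appendix 5, produces the primary endpoint and is the study's main invasive procedure. Its harms are the ones the AE definition handles worst. AE status also has consequences elsewhere: it triggers follow-up in 8.3 and is named among the withdrawal criteria in 8.1.

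**Working it through.** The plan states no figure to reproduce. The check applies the two definitions in 8.0 to each kind of event and then counts the exposure.

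**Step 1. Literal classification.**

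| Event | AE? | SAE? | Follow-up required by 8.3? |
|---|---|---|---|
| Subject-reported, deemed related to Xifaxan, does not force discontinuation | Yes | No | Yes |
| Subject-reported, unrelated to Xifaxan, does not force discontinuation | No | No | No |
| Subject-reported, caused by balloon or lactulose test, does not force discontinuation | No | No | No |
| Seen only by staff, does not force discontinuation | No | No | No |
| Subject-reported, unrelated or procedure-caused, forces discontinuation | No | Yes | Yes |

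**Step 2. Comparison with the causality text.** If the definition governs, *Not* and *Unlikely* can never be assigned to an AE, and a study procedure can never be the sole cause of one. If the causality text governs, rows 2 and 3 are AEs. Two staff members who each follow a different sentence of 8.0 would record different events.

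**Step 3. Timing.** One causality factor in 8.0 is that the event should come after the therapy. Between Day -7 and Day 0 no Xifaxan has been supplied, so nothing arising then can be deemed related to it. Participation runs from Day -7 to Day 15, which is 15 - (-7) = 22 days. The pre-drug period is 7/22 = 32% of that time. In it an SAE is possible but an AE is not. On Day 15 the position differs: an event after the second balloon test could still be attributed to Xifaxan and so count, but it drops out if it is attributed to the balloon.

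**Step 4. Exposure.** Section 3.3 plans 40 consented subjects and 15% dropout.

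- Day -7 balloon tests: up to 40.
- Day 15 balloon tests: 40 × (1 - 0.15) = 34 with the planned dropout, 40 without.
- Total: 40 + 34 = 74, up to 40 + 40 = 80. The budget's 80 paid visits match the upper figure.

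The same counts apply to the lactulose test. They are numbers of procedures, not of missed events.

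**Step 5. The SAE side.** Section 8.4 asks for reporting once an event meets the protocol's SAE definition, which turns on discontinuation. The seriousness field in the same 8.4 report is based on outcomes, including hospitalization. A hospitalization unrelated to the drug that does not force discontinuation fits the 8.4 list, yet under 8.0 it is neither SAE nor AE.

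**The case against.** The strongest reply is that the later text of 8.0 shows that unrelated and procedure-caused events were meant to be recorded, so the definition is only loosely worded. That is probably the intention, and it stands as a limit: the loss follows from applying one sentence literally and is not a stated aim. It does not remove the contradiction, and the causality text is a weak basis for overriding the definition because it names a different product.

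A reader might infer three stronger things that the documents do not support.

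- *Procedural or unrelated harm has no route into the safety data.* The SAE line keeps such events if the subject reports them and they force discontinuation.
- *The independent monitor would never hear of balloon harm.* Section 8.0 sends all side effects to the monitor, and that term is not itself limited to Xifaxan. Whether balloon harm is included is unclear; it is not excluded.
- *The reported AE rate will be biased low.* It could be, if staff follow the definition. No complication rate is given from which to estimate by how much.

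It is also fair to say that no AE rate is a primary or secondary outcome in section 7 and that the primary paired comparison is unaffected. The content of the flowchart in 6.3 and the AE and SAE forms cannot be seen, so enquiries about events may be scheduled there. Day 15 is the last contact listed in 6.2, and 6.4 gives 3 weeks per subject, but 3.3 describes a 4-month follow-up. The absence of later contact therefore cannot be asserted.

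**Conclusion.** The point holds as an internal contradiction in 8.0 with a practical consequence. Followed as written, the AE definition leaves out three kinds of non-discontinuing event: those unrelated to the drug, those caused by the balloon or lactulose test (including everything from Day -7), and those seen only by staff. Such events need not be followed under 8.3, and the recorded AE count could be too low. The affected exposure is about 74 to 80 balloon tests, up to 40 of them before any drug. The size of any under-count is unknown.

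This rests on two assumptions: that staff apply the definition literally, and that no broader definition stands in material that cannot be seen. No other section of the visible text gives one. The effect is on the safety record, not on the efficacy analysis.

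**What to change.** 1. In 8.0, define an AE as any untoward event from the first study procedure (Day -7) onward, whether reported by the subject or observed by staff, and regardless of relationship.
2. Assess relationship separately to Xifaxan, to the balloon test and to the lactulose test, using the existing four categories. Word the timing factor so that it refers to whichever exposure is being judged; otherwise it does not suit the Day -7 tests.
3. Replace the medical food supplement wording in section 8 with the actual study product.
4. Reconcile the SAE definition in 8.0, which depends on subject report and on discontinuation, with the seriousness list in 8.4.

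Asking about events at Day 0 and Day 15 is a low-cost addition to 6.2. A telephone contact after Day 15 is optional and is not needed to resolve the contradiction; it would mean at most about 40 short calls by the coordinator already in the budget.

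The cost is a wording amendment to section 8 and a matching change to the AE form. The downside is that more minor, unrelated events will be listed.

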8.1 Clinical criteria for withdrawing an individual subject from the study

Clinical criteria for withdrawing an individual subject from the study are as follows:

- Subject chooses to withdraw
- The occurrence of an adverse event, which, in the judgment of the Investigator or independent monitor, suggests an unacceptable risk to the subject
- Pregnancy
- Investigator discretion
- Subject noncompliance

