8.2 Criteria for stopping or changing the study protocol

Criteria for stopping or changing the study protocol due to safety concerns are as follows:

- Should the investigator, independent monitor, the FDA, or local regulatory authorities become aware of conditions arising during the conduct of this study that may warrant the cessation of the study, such action may be taken. Prior to such action, consultation between the investigator, and, as appropriate, the FDA and/or local regulatory authorities will take place
- If there are >2 subjects with serious adverse events, the independent study
 monitor will examine and audit the cases and determine the relevance to the
 assigned study medical food supplement and whether the trial should continue
 or if there are grounds for discontinuing the study

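### The only SAE definition (8.0) depends on forced discontinuation, so a hospitalization or disabling event in a subject who continues requires no 24-hour report and adds nothing to the 8.2 count

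*Combined protocol and SAP*

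**What the plan says.** Section 8.0 sorts side effects into two classes. An AE is a subject-reported event that is "deemed related to Xifaxan but may or may not prevent continuation of the trial"; the examples are body aches and loose stool. An SAE is an event reported during the trial which "may or may not be deemed related to Xifaxan that forces discontinuation of the trial"; the example is anaphylaxis. Neither definition mentions outcome.

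Section 8.4 requires prompt reporting to the supplier once the investigator judges that the protocol's SAE definition is met, with the information sent within 24 hours of the investigator learning of the event. The required content includes a seriousness field with six entries: fatal, life threatening, hospitalization, congenital anomaly, disabling, and other.

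Section 8.2 sets a study-level trigger: "If there are >2 subjects with serious adverse events", the independent monitor audits the cases and considers whether the trial should go on. It does not define the term again.

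Four other provisions bear on the same events:
- Section 8.0: "All side effects will be reported to a data safety monitor who is independent of the study". No deadline is given.
- Section 8.1 allows withdrawal for "The occurrence of an adverse event, which, in the judgment of the Investigator or independent monitor, suggests an unacceptable risk to the subject". The note closing 4.2 makes developing an exclusion criterion a basis for discontinuation.
- Section 8.2 also lets the investigator, the monitor or regulators respond to "conditions arising during the conduct of this study that may warrant the cessation of the study, such action may be taken".
- Section 8.5 has pregnancies reported promptly, with updates as soon as they are known, and outcomes collected to term, including birth defects.

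On causality, 8.0 provides grades for events that are not, or are unlikely to be, related. The lower of the related-sounding grades, unlikely, "is considered not related to the study medical food supplement". It adds: "Study procedures should also be considered as possible causes of an AE".

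**The concern.** The duty to report within 24 hours and the count that starts the monitor's audit both depend on the 8.0 definition. That definition asks whether the subject stopped, not what happened to the subject. The seriousness field in 8.4 suggests that the authors meant to capture hospitalization, life threat and disability, but an event reaches that field only after passing the discontinuation test. What is at stake is an expedited safety report that the protocol does not require for outcomes its own report form treats as serious.

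There is a secondary problem in the AE definition. It requires relatedness to Xifaxan, whereas the causality text in the same section grades AEs as unrelated and names study procedures as possible causes. An event cannot be an AE only if related and also be an AE graded unrelated.

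**Working it through.** There is no stated figure to reproduce. The check traces events through the sections as written.

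**Inputs.** SAE test: forced discontinuation (8.0). Report trigger: the protocol's SAE definition, hence 8.0 (8.4). Audit trigger: more than 2 subjects with SAEs, that is 3 or more (8.2). AE test: deemed related to Xifaxan (8.0). Schedule: balloon test at Day -7, drug supplied at Day 0, second balloon test at Day 15 with no later visit listed (6.2); 3 weeks' involvement per subject (6.4).

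**Step 1: trace individual events**, reading discontinuation as the subject's own.

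| Event | SAE under 8.0? | 24-hour report required? | Adds to 8.2 count |
|---|---|---|---|
| Hospitalization, subject continues | No | No | 0 |
| Life-threatening or disabling event, subject continues | No | No | 0 |
| Hospitalization that begins after the Day 15 visit | No: no participation is left to discontinue | No | 0 |
| Hospitalization leading to withdrawal under 8.1 or the 4.2 note | Arguably yes | Yes | 1 |
| Minor event that forces the subject to stop | Yes | Yes | 1 |

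The first three rows are the gap. The fourth marks its limit. The fifth shows that the definition also admits events that fit none of the named outcomes in 8.4.

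**Step 2: the 8.2 count.** Suppose three subjects are hospitalized and all continue. Under 8.0 the count is 0 and no audit is triggered. If the outcomes in 8.4 defined seriousness, the count would be 3, which exceeds 2, and the audit would start. Three subjects are 3/40 = 7.5% of the 40 to be consented (3.3), so even an outcome-based definition would need several such events in a short study before the count mattered.

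**Step 3: the AE definition.** The Day -7 balloon test takes place before any Xifaxan is supplied, so an event caused by it cannot be related to the drug and falls outside the AE definition. If it does not force discontinuation, it falls outside the SAE definition too. The same holds for an unrelated hospitalization in a subject who continues. Yet 8.0 tells the investigator to weigh study procedures as causes of an AE.

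**Step 4: whose discontinuation?** The wording could mean the subject's participation or the whole study. On the second reading the gap is wider, because even an event that made one subject withdraw would not qualify. That reading fits poorly with 8.2, which expects more than two subjects with SAEs while the trial's continuation is still undecided. The subject reading is therefore used here, but the text does not settle it.

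**The case against.** The strongest reply is that the gap is narrow and other routes cover much of it. Many serious events would lead to withdrawal under 8.1, or would create an exclusion criterion such as an uncontrolled significant medical condition. Those events can meet 8.0 and start the 24-hour clock. This stands, and it confines the point to events that do not lead to discontinuation.

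Side effects also go to the independent monitor, and 8.2 permits discretionary action. This stands as mitigation, but the monitor route has no stated deadline, is not the report to the supplier, and does not feed the count.

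It can also be said that 8.4 does not contradict 8.0, since its list is a data field in a report already triggered and not a second definition. That is right. The defect is a narrow trigger beside a field list that points to a broader intent. An investigator might well infer that intent, also from the anaphylaxis example, and report a hospitalization anyway; the text does not require it.

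A reader might cite the congenital-anomaly entry as the clearest failure, since an anomaly found at birth comes after a 3-week participation. The documents do not support leaning on it: pregnancy is itself a withdrawal criterion in 8.1, and 8.5 has its outcome passed on as soon as it is known.

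On the AE definition, 8.0 says that all side effects are captured, and its SAE bullet expressly includes unrelated events. A sensible investigator would probably record procedure-related events. This makes the AE item secondary, but does not remove the contradiction.

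**Conclusion.** The point holds on the text as supplied. A rule that is stated, not merely left out, gives the wrong safety result when followed: serious outcomes in subjects who continue, or that begin after the last visit, carry no 24-hour reporting duty and do not enter the 8.2 count.

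Its size cannot be put in numbers. The documents give neither a rate of serious events nor the share of affected subjects who would continue. A reader might infer that such reports will be missed, or that the events will go unseen. Neither follows: a report that is not required may still be sent, and the monitor receives side effects. Nor is the audit trigger seriously weakened; given the 3-subject threshold and about 40 subjects, the effect on the 8.2 count is likely small. The consequence lies mainly in the 24-hour report. No efficacy estimate or test is affected.

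The conclusion rests on four assumptions: that 8.0 is the only SAE definition (8.0 mentions an SAE form that is not in the supplied text); that discontinuation means the subject's; that Day 15 is the last visit, as 6.2 and 6.4 indicate, although 3.3 speaks of a 4-month follow-up; and that the medical food supplement named in the causality text means the study drug.

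**What to change.** - Reconcile 8.0, 8.2 and 8.4 around one SAE definition that includes the outcome categories already printed in 8.4 and does not depend on discontinuation.
- State that this definition drives both the 24-hour report and the 8.2 count. The 8.2 threshold and the action it prompts remain the sponsor's decision.
- Remove the relatedness condition from the AE definition, so that it agrees with the causality grades and the study-procedure text and covers events from the Day -7 balloon test.
- State whether the discontinuation referred to in 8.0 is the subject's or the study's.

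The cost is protocol wording and slightly more event recording and reporting in about 40 subjects, each followed for about 3 weeks. Sample size, endpoint and the paired analysis stay as they are.
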